1.1 Background

Total knee arthroplasty (TKA) is a frequently performed procedure and is expected to increase in numbers due to the aging population and growing obesity rates [1-6]. Fast-track regimes with multimodal opioid-sparing analgesia have improved postoperative outcomes [7, 8]. However, a subset of patients still experiences unsatisfactory levels of postoperative pain in the weeks following surgery [9-12], potentially delaying mobilization and recovery as well as increasing the need for opioid analgesics. Current recommendations for pain management following TKA according to the Procedure Specific Postoperative Pain Management (PROSPECT) Working Group include paracetamol, nonsteroidal anti-inflammatory drugs (NSAIDs), glucocorticoids, local infiltration analgesia, and single shot adductor canal block (ACB) [12]. However, the role of ACBs for pain after TKA has been under extensive debate in recent years. While an ACB may provide some pain relief, the duration of pain control is usually less than 24 h and the effect on length of stay (LOS) and opioid consumption is questionable [12].

In the past decades, cryoneurolysis has been used to treat acute pain following herniorrhaphy [13], tonsillectomy [14], and thoracotomy [15] via the surgical incision. The emergence of percutaneous cryoprobes and the use of ultra-sound guided techniques has allowed for an increase in potential applications [16]. Recently, the use of cryoneurolysis has gained attention as a potential regional anesthetic technique for the treatment of knee pain. Cryoneurolysis works by freezing peripheral nerves with temperatures in the range of -20°C to -100°C, causing a Wallerian degeneration of nerve axons distal to the treatment site [17]. This process involves loss of the relative continuity of the axon and its covering of myelin but with a preservation of the surrounding endo-, peri-, and epineurium, thus allowing normal axonal regeneration and remyelination. Axons regenerate at a rate of 1-2 mm/day. Thus, resulting in a nerve block that typically will resolve with full recovery within weeks to months depending on the site of treatment [17].

The effect of cryoneurolysis on knee pain has been documented in a few studies. A randomized, double-blind, sham-controlled trial found that cryoneurolysis reduced symptoms of knee osteoarthritis for up to 150 days [18]. A retrospective chart-review of 100 patients undergoing TKA found that cryoneurolysis significantly lowered LOS, reduced opioid consumption until 12 weeks after surgery, and reduced pain at the 2- and 6-weeks follow-up [19]. Another retrospective analysis in 267 patients undergoing TKA found a comparable reduction in opioid requirements, pain, and LOS in patients treated with cryoneurolysis compared with historic controls [20]. A recent RCT comparing cryoneurolysis to standard of care in 124 patients undergoing TKA found that cryoneurolysis reduced opioid consumption at 72 h, 6 weeks and 12-week follow-ups [21].

Although these findings are promising, cryoneurolysis is expensive and comprehensive, and might not be relevant in all patients receiving multimodal analgesia with COX-2 inhibitors, paracetamol, local infiltration analgesia, and high-dose steroid in a fully implemented enhanced recovery program [22, 23]. Several risk factors have been associated with a high pain response including age, gender, preoperative pain, psychological profile, and quantitative sensory testing (QST) [24-26]. However, when including postoperative pain in

the prediction of acute pain, movement-evoked pain 24 h postoperatively is the best predictor for pain the week following surgery [[name] et al. – IN PREPARATION].

Using postoperative pain 24 h after surgery as a predictor of a sustained high pain response, we hypothesized that postoperative cryoanalgesia compared to a local anesthesia (LA) block with sham cryo treatment would reduce pain in patients with moderate to severe pain following TKA 2-7 days after surgery.

2. Aim

To compare the effect of postoperative cryoanalgesia with a sham treatment consisting of LA block only on postoperative pain in the first week after surgery in TKA patients with moderate to severe pain on the first postoperative day.

3. Outcomes

3.1 Primary outcome

Cumulated pain (VAS 0-100 mm) upon ambulation in a 5-meter walk test on days 2-7 postoperatively after TKA surgery.

3.2 Secondary outcome

- Pain (VAS 0-100) during rest and during 5-meter walk test at the 2 weeks, 4 weeks, 12 weeks, and 24 weeks follow-up
- Pain relief immediately following blockade evaluated as Δ VAS 0-100 during a 5-meter walk test before and after the blockade
- Cumulated pain at rest and during night from days 2-7
- Quality of sleep and nausea postoperatively from days 2-7
- Cumulative use of rescue-analgesics from days 2-7, and at 2 weeks, 4 weeks, 12 weeks, and 24 weeks follow-up
- Oxford knee score at 12 weeks
- LOS in hospital, and reasons for prolonged stay (>1 postoperative day) registered as “Why still in hospital”
- Reasons for re-admissions within 12 weeks
- Morbidity and mortality (4-, 12-, and 24 weeks follow-up by Electronic Patient Journal (EPJ) or telephone)

4. Study design

Randomized, participant- and observer-masked, sham-controlled trial.

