5.2 Exclusion criteria

- Ongoing treatment of systemic glucocorticoids or other immunosuppressant treatment apart from inhaled steroids
- Insulin-dependent diabetes
- Pregnancy or breastfeeding*
- Mental disability that could impair a patient's decision-making capability of giving informed consent and not enabling valid data collection.
- Patients with known diagnoses of schizophrenia, ongoing psychosis, bipolar disease and/or a history of ongoing anti-psychotic treatment.
- Patients with modulated pain-reception (experience) based on other diseases or injuries, e.g. spinal cord or brain injury, severe polyneuropathies or neurologic disorders.
- Posttraumatic osteoarthritis as reason for TKA
- Bleeding disorder
- Localized infection in the treatment area

- Cryoglobulinemia, cold urticaria, paroxysmal cold haemoglobinuria, or Raynaud's syndrome
- Perioperative peripheral nerve block

*Pregnancy: No women with suspected or proven pregnancy are eligible for inclusion. The following will be considered as safe contraception: intrauterine device or hormonal contraception. For women aged between 18-50 years, a urine HCG test for pregnancy will be performed.

6. Randomization and blinding

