7.2 Data analysis

All participants who meet the inclusion criteria and undergo randomization will be included in the intention-to-treat (ITT) population. The per-protocol (PP) population is defined as the group of patients who are randomized, receive the treatment to which they were randomly assigned, and complete their assessments without any major protocol deviations. The primary and secondary outcome analyses will each be performed for the ITT and PP populations. The primary endpoint along with other continuous data will be tested using independent samples t-test or Mann-Whitney U test as appropriate. The secondary outcomes will also be analyzed relative to the pain relief during the initial LA injection in the cryo group versus the remaining patients from both groups. A P -value < 0.05 is considered significant. Dichotomized data will be tested using Chi-square or Pearson's exact test. Uni- and/or multivariate analysis, where appropriate, will be made to test for independent variables. Missing values will be accounted for in the final statistical plan. Statistical calculations will be made using either R statistical software (Open source) or SPSS statistics (IBM, New York, USA).

The study will be registered at Clinicaltrials.org and will include a complete statistical analysis plan submitted to publication.

8. Study plan

A general layout of the study is provided in Appendix 1. In the outpatient clinic, the screening procedure will be performed among patients planned for TKA by the surgeons. Patients will be asked by orthopedic staff whether they may be contacted regarding the research project. The research staff will then contact potential patients either in person or via telephone. The written study information will be explained – either at the outpatient clinic or via telephone by the investigator.

All patients receive both spoken and written information. Information is given in a separate closed room without interruptions. All patients are given the chance of an additional meeting with the chance of bringing a relative. All patients must give a signed informed consent on paper prior to inclusion to participate in the study. The patient will sign the consent form on day 1 after surgery.

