8.1.4 Standard postoperative treatment

The postoperative multimodal analgesic regimen consists of:

Celebra 200 mg x 2, for 7 days.
Paracetamol 1 g x 4, for 7 days.
Morphine 10-20 mg or opioid equivalents administered only as rescue opioids.

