8.3 Study specific

Pain is rated by the patient before the intervention, after the initial LA injection, at home on days 2-7 and at the 2-, 4-, 12-, and 24 weeks follow-up via telephone.

A Visual Analog Scale (VAS 0-100) is used. On days 1-7 patients mark their pain in the electronic CRF twice a day (Appendix 5). If the patient is not able to complete the ratings electronically, a physical pain diary will be provided. Pain is rated by the patient at rest, during a 5-meter walk test, and during sleep. At the hospital and at the follow-ups patients are asked to rate their pain at rest and during a 5-meter walk test.

Use of rescue-analgesics (opioids) or other specific pain-relieving actions that differ from standard treatment is noted in the CRF.

The presence of dysesthesia or other side effects will be evaluated at each follow-up.

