8.4 Other clinical data

- Demographical data (gender, age, height, weight, co-morbidity, American Society of Anesthesiologist (ASA) score)
- Preoperative opioids/strong analgesics
- Pain Catastrophizing Scale (PCS)
- Surgical data (date of surgery, indication, surgical time, procedure information, intraoperative bleeding, transfusion data, perioperative analgesics)
- Type and dosage of analgesics.
- Deviations from standard treatment
- Quality of sleep, lethargy, dizziness, and nausea, pre- and postoperative registration, on a NRS (0-10)
- Adverse events throughout the hospitalization and at each follow-up
- Neuropathic Pain Scale for Postsurgical Patients (NeuPPS)

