13.2 Informed consent

The information will be given without disturbance and interruptions and the patient is informed that he/she can schedule a new information interview and to bring a bystander/relative if wished. The information interview will be postponed until the bystander is present if requested. The information interview can be by attendance at the facility or by phone.

The patient receives the written information for participants at the pre-surgery appointment or if needed by secure email. The patient is informed that he/she is entitled to at least one day of reflection/consideration. If the patient does not want to participate, they can do so without informing about the reason for this.

The investigator or research-nurse informs the patient and collect the signed consent form. When needed, in case of sickness or holiday, other research collaborators can collect the signed consent form. The signed consent will be done before the surgery. Both the hospital and the patient will have a signed Consent form. The applicable guidelines and restrictions concerning informed consent brought by the National Ethics Committee is attached to the patient-information. Information for the participant and the Consent form is attached as Appendices 2 and 3.

The patient will be informed that participation is voluntary, and that withdrawal can happen anytime without justification, also after the signed consent, without this affecting their further treatment course and stay at the facility. They will also be informed that the investigator can pull them out of the study anytime at their discretion.

14. Information from the electronic patient journal

All information from the EPJ will be obtained after signing the informed consent form the day after surgery. The consent gives the primary investigator, the sponsor, and sponsor's representatives direct access to gather information from the patient's journal including the EPJ. The information obtained is necessary for the completion of the study and to make sure that the study is carried out correctly, which includes self-control and quality control. After the informed consent, the following information will be obtained from the patient's EPJ:

- Gender
- Age
- Height
- Weight
- Co-morbidities
- American Society of Anesthesiologist (ASA) score

- Pain Catastrophizing Scale (PCS)
- Current medical prescriptions (including glucocorticoids, immunosuppressants, opioids, insulin, and anti-psychotics)

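### Rescue-analgesic totals, and the sleep and nausea scores, are compared without the preoperative values already recorded, and no rule says how a patient's usual opioid is counted.

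*Combined protocol and SAP*

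**What the plan says.** The outcome in section 3.2 is "Cumulative use of rescue-analgesics from days 2-7, and at 2 weeks, 4 weeks, 12 weeks, and 24 weeks follow-up". No unit, conversion between opioids or handling of baseline use is given.

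Section 8.1.4 allows opioids in the standard regimen in one form: "Morphine 10-20 mg or opioid equivalents administered only as rescue opioids". Section 8.3 describes the recording: "Use of rescue-analgesics (opioids) or other specific pain-relieving actions that differ from standard treatment is noted in the CRF". Neither mentions an opioid that the patient already took before surgery and continues.

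Section 5.2 excludes on some current medication, for example "Ongoing treatment of systemic glucocorticoids or other immunosuppressant treatment apart from inhaled steroids", but has no item on opioids, so habitual users can enter. The plan collects their use: section 8.4 lists "Preoperative opioids/strong analgesics", and the record extraction in section 14 includes "Current medical prescriptions (including glucocorticoids, immunosuppressants, opioids, insulin, and anti-psychotics". Section 8.4 also has "Quality of sleep, lethargy, dizziness, and nausea, pre- and postoperative registration, on a NRS (0-10", so the days 2-7 sleep and nausea outcomes have a baseline.

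For the analysis, section 7.2 says: "The primary endpoint along with other continuous data will be tested using independent samples t-test or Mann-Whitney U test as appropriate". It also allows univariate or multivariate analysis where suitable, but names no covariate and no outcome. Section 6.1 describes block randomisation and mentions no stratification.

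**The concern.** A usual opioid taken every day adds the same kind of milligrams to the total as rescue doses do, and it has nothing to do with allocation. If it is counted, it adds variance, and in a trial of 44 a handful of users can easily fall unevenly between the arms. If it is not counted, the plan needs a rule, because otherwise two staff members could code the same patient differently.

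The outcome is secondary, but it carries weight. Section 11.2 starts from the premise that rescue-opioid use can be reduced. Rescue is also available in both arms, so opioid intake is needed to interpret the pain result. A noisy comparison could miss a real reduction in opioid use although the trial already holds the variable that would remove much of the noise. The sleep and nausea comparisons leave their recorded baseline unused in the same way.

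**Working it through.** **The plan's own figure.** The only sample size is for walking pain (section 7.1): mean 390, SD 208, a 50% reduction (195), two-sided 0.05, power 80%. n per arm = 2 × [208 × (1.960 + 0.842) / 195]² = 17.86, rounded up to 18. This reproduces the plan. There is no corresponding calculation for opioid use, so what follows rests on assumptions.

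**Assumed inputs (none in the documents).** 10-20% habitual users, 15-60 mg oral morphine equivalents per day, rescue intake over days 2-7 with mean 120 mg and SD 60 mg, true difference 40 mg. From the plan: 22 per arm, and 6 days in the period.

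**Chance imbalance.** The number of users falling in one arm is hypergeometric (44 patients, k users, 22 drawn).
- k = 4: the arms differ by at least 2 users with probability 61%; all 4 fall in one arm with probability 11%.
- k = 6: a 4:2 or worse split has probability 66%; 5:1 or worse, 18.5%.

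At 30 mg/day, a 4:2 split moves the arm difference over days 2-7 by 2 × 30 × 6 / 22 = 16 mg, against the assumed true difference of 40 mg.

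**Added variance, by hand.** A user share p at d mg/day adds variance p(1 − p)(6d)² to 60² = 3,600. The standard error of the difference is SD × √(2/22) = SD × 0.3015.
- No users: SE = 60 × 0.3015 = 18.1; 40/18.1 = 2.21; power ≈ Φ(2.21 − 1.96) = 60%.
- 10%, 15 mg: SD = √(3,600 + 0.09 × 90²) = 65.8; SE 19.8; power ≈ 52%.
- 20%, 30 mg: SD = √(3,600 + 0.16 × 180²) = 93.7; SE 28.3; power ≈ 29%.
- 20%, 60 mg: SD = √(3,600 + 0.16 × 360²) = 156; SE 47.0; power ≈ 13%.

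**Simulation of the same model** (3,000-4,000 runs per scenario, intake truncated at 0):

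| Users, daily dose | t-test | Mann-Whitney | Adjusted for preoperative dose |
|---|---|---|---|
| none | about 58% | 57% | about 58% |
| 10%, 15 mg | 50% | 49% | 56% |
| 10%, 30 mg | 36% | 42% | 57% |
| 15%, 30 mg | 31% | 36% | 59% |
| 20%, 30 mg | 26% | 30% | 56% |
| 20%, 60 mg | 12% | 28% | 56% |

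**A skewed alternative.** With exponential rescue intake (mean 100 units in sham, half that in cryo) and 2, 4 or 6 users each adding about 180-720 units, power for t-test / Mann-Whitney goes from 58% / 50% with no users to 10-45% / 29-43%. Adjustment keeps it near 55%. With 4 users adding 360 units, the standard error rises from about 24 to 42 units and returns to 24 when adjusted.

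**Bias and type I error.** In the skewed model the average unadjusted estimate stays near the true −50 throughout. With no true effect, rejection rates for all three analyses are 3.7-6.1% there, and in the first model 4.3-5.5% for the two named tests.

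**Sleep and nausea.** A baseline covariate correlated ρ with the outcome cuts the residual variance by a factor of about 1 − ρ². The documents give no ρ, so no size is claimed.

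**The case against.** A reader might infer that the plan counts every opioid as rescue. The documents do not say so. Section 8.1.4 speaks of opioids given as rescue, which a usual prescription is not, and section 8.4 lists preoperative opioids and the type and dose of analgesics as separate items, so the data might allow a split. What stands is the silence: no rule is stated either way.

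A reader might also infer that the planned test could manufacture an opioid reduction. It does not do so at more than its nominal rate. Preoperative use precedes randomisation, the average estimate is unbiased, and chance imbalance is already covered by the test's error rate. The cost is in precision.

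The lowest power figures belong to the t-test. Section 7.2 also offers Mann-Whitney, the usual choice when a few values are extreme, and in the worst scenario it more than doubles power (28% against 12%). That objection is right, but both named tests fall well short of the adjusted analysis once use is more than light.

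Adjustment is not ruled out either, since section 7.2 permits multivariate analysis and promises a complete analysis plan. With no covariate or outcome named, however, nothing is prespecified.

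The adjusted figures are a best case, because the simulation treats usual intake as additive and fully known. Extending the arithmetic to days 8-168 gives 2 × 30 × 161 / 22 = 439 mg for a 4:2 split. This assumes an unchanged dose for 23 weeks, and the documents give no SD to set it against, so no weight is placed on it.

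Finally, the aim in section 2 is pain. Opioid use is one of nine secondary items and has no power claim, and its power is only about 58% under these assumptions even with no users.

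**Conclusion.** The point holds as a gap in definition and efficiency for secondary outcomes. Habitual users are eligible, no rule says whether their usual opioid counts, and the named tests leave recorded baselines unused. Under the assumed inputs, power for the days 2-7 opioid comparison falls from about 58% with no users to 12-50% (t-test) or 28-49% (Mann-Whitney), against about 56% at best with adjustment. At the light end (10% users, 15 mg/day) the loss is small; at the heavy end it is large. Where this trial will fall cannot be told from the documents, and if usual opioids are in practice left out of the totals, the variance problem shrinks and only the missing rule remains.

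The documents do not support a claim of systematic bias, of an inflated type I error, or of a written rule that all opioids are rescue. The primary endpoint and its sample size are unaffected.

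**What to change.** In section 7.2, and in the analysis plan it promises:

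- State how a usual preoperative opioid is counted in the rescue-analgesic outcome, and give the unit (morphine equivalents) and the conversion source.
- Compare total opioid intake between arms in a model with preoperative opioid use as a prespecified covariate. If the distribution is too skewed, use a rank test stratified by preoperative use (yes/no).
- As a sensitivity analysis, report intake excluding the usual opioid, or the comparison in opioid-naive patients.
- Use the recorded preoperative score as covariate for the days 2-7 sleep and nausea outcomes.

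Total intake is preferable as the main quantity to intake above the preoperative dose. Subtraction changes the outcome, and it needs a further rule for patients who take less opioid after surgery than before.

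The cost is wording and one covariate per outcome, all already collected. Sample size, visits and treatment do not change. One small burden is added: if dose is the covariate, the preoperative opioid dose must be entered as a number.

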4.2 Number of patients

44 patients, 22 in each group (sham-group vs. cryo-group).

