6.1 Randomization

Using <https://www.sealedenvelope.com/>, a randomization will be carried out using 2:2 block-randomization, half of which will be allocated to the sham-group and the other half to the cryo-group.

It is not possible to perform the cryoneurolysis while being blinded. Thus, the anesthetist performing the intervention will be unblinded. However, the patient and all personnel involved in study-specific assessments will be blinded to the allocation.

Group 1: sham-group	Postoperative ultrasound guided nerve block with LA followed by sham cryoneurolysis of the superficial genicular nerves.
Group 2: cryo-group	Postoperative ultrasound and guided nerve block followed by cryoneurolysis of the superficial genicular nerves.

<https://www.sealedenvelope.com/> will generate unique randomization codes to be imported to REDCap. Two lists containing the unique randomization codes will be made and stored at the Dept. of Anesthesiology, Hvidovre Hospital.

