7.1 Power calculation

Data from our previous study showed that pain during a 5-meter walk test at 24 h was the best predictor of cumulated pain on days 2-7 after TKA surgery [[name] et al. – IN PREPARATION]. With the optimal cut-off of VAS ≥ 45 , the mean (SD) cumulated pain during a 5-meter walk test on days 2-7 was 390 (208). A 50 % reduction in cumulated mean VAS upon mobilization days 2-7 postoperatively is clinically relevant. In a two-sided superiority design with a level of significance of 0.05 and a power of 80% we need two groups of 18 patients each. Assuming a small number of dropouts, 22 patients will be included in each of the two groups resulting in inclusion of 44 patients in total.

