8.4.1 Neuropathic Pain Scale for Postsurgical Patients

The NeuPPS consists of 5 yes/no questions about the presence of sensory disturbances [31, 32]. A score of 1 will be assigned for a 'yes' and a score of 0 will be assigned for a 'no'. The summed scores are used. The patients will fill out this questionnaire preoperatively and at every follow-up.

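### The visible plan gives no preoperative Oxford knee score, so the 12-week comparison gives up some precision and chance baseline imbalance cannot be examined or adjusted for

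*Combined protocol and SAP*

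**What the plan says.** Section 3.2 names "Oxford knee score at 12 weeks" among the secondary outcomes. This is the only mention of the instrument in the visible text, and no other knee-function score is listed; the 5-meter walk test is there to rate pain.

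The data-collection lists (8.3 study-specific data, 8.4 other clinical data, 10.1 source data in the CRF, 14 data from the patient journal) contain no preoperative Oxford knee score. They do not contain the 12-week score either. Appendix 1, the general study plan, appears by title only.

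Other patient-reported measures do have a stated preoperative assessment. For NeuPPS the plan says "The patients will fill out this questionnaire preoperatively and at every follow-up". Section 8.4 asks for sleep, lethargy, dizziness and nausea before as well as after surgery. The Pain Catastrophizing Scale is completed before surgery as local routine.

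Section 7.2 assigns continuous outcomes to an independent-samples t-test or a Mann-Whitney test. It also allows univariate or multivariate analysis where appropriate, without naming a covariate, and promises a complete statistical analysis plan. Section 4.2 sets 22 patients per arm. Under 6.1, "a randomization will be carried out using 2:2 block-randomization", with no stratification factor named.

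**The concern.** Where preoperative and 12-week function are correlated, part of the spread in the 12-week score reflects how limited each knee was before surgery. An unadjusted test leaves that spread in the error term. A preoperative score used as a covariate removes it, and with 22 per arm there is little precision to spare.

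The generic covariate wording in 7.2 cannot help, because a model cannot adjust for a value that was not recorded. Once a patient has had surgery, the preoperative score can no longer be collected prospectively. If the arms happen to differ at baseline, nobody will be able to see it or account for it.

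At stake are the width of the confidence interval for the trial's only knee-function score, and how readily a reader can interpret a null or a modest difference at 12 weeks.

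**Working it through.** **The plan's own figure.** Section 7.1 gives a mean of 390 and SD of 208 for the primary outcome, and states "A 50 % reduction in cumulated mean VAS upon mobilization days 2-7 postoperatively is clinically relevant". The target difference is 0.5 × 390 = 195, or 195/208 = 0.9375 SD. With two-sided alpha 0.05 and 80% power, n per arm = 2 × (1.960 + 0.842)² / 0.9375² = 17.9, rounded up to 18. This matches the stated 18 (an exact t calculation gives 19). The plan raises it to 22 for dropout. It gives no SD, target difference or power for the Oxford knee score, so what follows is in units of that score's SD and uses the same normal approximation.

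**Inputs.** n = 22 per arm (4.2); two-sided alpha 0.05 and 80% power (7.1); pre-post correlation r, not in the documents, shown for r = 0.2 to 0.7.

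**Unadjusted comparison.**
- Standard error = √(2/22) = 0.302 SD.
- Detectable difference = (1.960 + 0.842) × 0.3015 = 0.845 SD.

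**ANCOVA on the preoperative score.** The variance is multiplied by (1 − r²), so the detectable difference is 0.845 × √(1 − r²) and the equivalent unadjusted sample size is 22/(1 − r²). The power column is for an effect that the unadjusted test would detect with 80% power.

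| r (assumed) | Variance factor | Detectable difference (SD) | Equivalent n per arm | Power |
|---|---|---|---|---|
| 0.2 | 0.96 | 0.828 | 22.9 | 82% |
| 0.3 | 0.91 | 0.806 | 24.2 | 84% |
| 0.4 | 0.84 | 0.774 | 26.2 | 86% |
| 0.5 | 0.75 | 0.732 | 29.3 | 90% |
| 0.6 | 0.64 | 0.676 | 34.4 | 94% |
| 0.7 | 0.51 | 0.603 | 43.1 | 97% |

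Estimating the covariate slope costs a factor of about 1 + 1/(2 × 22 − 4) = 1.025 in variance. With it, power is about 83% at r = 0.3 and 89% at r = 0.5. If only 18 per arm are evaluable, the detectable difference is 0.934 SD unadjusted, 0.891 SD at r = 0.3 and 0.809 SD at r = 0.5.

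**Chance imbalance.** The difference in mean preoperative score also has a standard error of 0.302 SD. A gap above 0.3 SD arises in about 32% of trials of this size, and one above 0.5 SD in about 10%. With equal SDs, a 0.3 SD gap shifts the expected 12-week difference by 0.3r: 0.09 SD at r = 0.3 and 0.15 SD at r = 0.5, against a standard error of 0.30 SD.

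**Type I error.** In 40,000 simulated null trials at each r, the unadjusted t-test rejected in 5.1% (r = 0.3) and 5.2% (r = 0.5). Among trials with a baseline gap above 0.5 SD, it rejected in about 8% and 15%.

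**Why not a change score.** With equal SDs, its variance relative to the 12-week score alone is 2(1 − r): 1.4 at r = 0.3 and 1.0 at r = 0.5. Below r = 0.5 it would do worse than the current plan.

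**The case against.** **Absence is weakly shown.** The collection lists omit the 12-week score as well, although it is a declared outcome, so they are not complete for this instrument. A preoperative score might be in Appendix 1. This stands: the most that can be said is that the visible text does not state one. The plan does state the preoperative timing of NeuPPS explicitly and has nothing comparable for this score.

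**Randomisation already deals with imbalance.** A reader might infer that a 12-week difference could not be separated from a difference in preoperative function, or that the comparison has no protection from chance imbalance. The documents do not support either reading. Allocation is random, the unadjusted standard error already includes chance imbalance, and type I error stays near 5% overall. The raised rejection rates above apply only within the minority of trials with a large gap; they are not a bias of the design.

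**The gain may be small.** At r = 0.3 the detectable difference moves only from 0.845 to 0.806 SD, and even at r = 0.5 the trial can detect only large effects on this score. The 32% figure holds for any normally distributed baseline variable with 22 per arm, and the resulting shift is modest. All of this stands.

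**The remedy is not free.** Eligibility depends on pain about 24 h after surgery, so every preoperative candidate would have to complete the score, including many possibly never randomised. This stands as a cost, but the planned preoperative NeuPPS already carries the same burden.

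**A fuller analysis plan is promised.** It could name covariates, but it could not supply a score that was not collected.

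**Conclusion.** The point holds as a modest loss of precision on one secondary outcome. On the visible text, the Oxford knee score is planned only at 12 weeks and compared without baseline adjustment. The comparison is valid, and nothing here suggests bias or an uninterpretable result.

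Adjustment would lower the detectable difference with 22 per arm from about 0.845 SD to about 0.81 SD (r = 0.3) or 0.73 SD (r = 0.5), the equivalent of about 24 to 29 patients per arm. The gain is slight at r = 0.2 (4% of variance), material from about r = 0.5 (25%) and larger above that. These figures rest on an assumed correlation, a roughly linear relation between the two scores, the normal approximation and full follow-up.

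The primary outcome and its sample size are unaffected. If a preoperative score is already intended, for instance in Appendix 1, only the wording and the analysis need attention.

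**What to change.** - **Collection.** Have patients complete the Oxford knee score at the same preoperative contact as NeuPPS, and list both the preoperative and the 12-week score in 8.4.
- **Analysis.** In 7.2, specify ANCOVA of the 12-week score with the preoperative score as covariate, not a change score, and report the adjusted difference with a 95% confidence interval.
- **Consent timing.** Section 8 has the form signed on day 1 after surgery; 13.2 has it signed before surgery. These must be reconciled before any study-specific preoperative questionnaire can be relied on. The conflict already affects preoperative NeuPPS.

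The cost is a few minutes for each preoperative candidate, including those who never meet the 24 h pain criterion, and a minor amendment to two sections. No extra visit is needed.
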